## PRECIS

Background:

\* AZD2171 is an oral potent inhibitor of receptor tyrosine kinases which impact vascular endothelial growth factor-A (VEGF)

\* VEGF appears important in blood vessel formation and disease progression in prostate cancer

\* No known effective therapy in patients with progressive androgen-independent prostate cancer after treatment with docetaxel

## **Objectives:**

\* Primary objective of this study is to determine if AZD2171 is associated with a 30% 6 month probability of progression free survival in patients with metastatic AIPC as determined by clinical and radiographic criteria

\* Secondary objective of this study will be demonstration of biologic effect by the drug in the patient and on the tumor (when possible). Correlative studies will be conducted on serially obtained tissue biopsies and white blood cell collections.

\* Laboratory correlates will include elucidation of activation of components of the VEGFR2 and angiogenesis pathways and evaluation of endothelial cell adhesion molecules (released by damaged cells) using ELISA, pharmacogenetic analysis of KDR variants and single nucleotide polymorphisms, and pharmacokinetic characterization of AZD2171 activity.

## **Eligibility:**

\* Metastatic progressive androgen-independent prostate cancer.

- \* Prior treatment with docetaxel.
- \* May not have QTc > 470 msec

or >1+ proteinuria on 2 consecutive dipsticks no less than 1 week apart

#### **Design:**

\* Phase II trial with a two stage design. 12 patients enrolled in first cohort, if 2 or more are progression free @ 6 months than enroll up to 35 evaluable patients. The ceiling will be set at 37 to allow for inevaluable patients.

\* Starting dose 20 mg QD for all patients

\* Once two stage design is complete then prednisone 10 mg once per day will be given in combination with AZD2171. The total number of patients will be 23 for this portion of the protocol.

SC	CHEMA	(ALL TIMES ARE APPROXIMATED):	I
PF	RECIS .		II
1.	OB.	IECTIVES	. 1
	1.1.	Primary	
		Secondary	
		ooondary	
2.	BAC		1
	2.1	Androgen-independent Prostate Cancer	
	2.2	AZD2171	
	2.3	Rationale	
3.	PAT	IENT SELECTION	. 8
-	3.1	Eligibility Criteria	
	3.2	Exclusion Criteria	
	3.3	Inclusion of Women and Minorities	
	3.4	Baseline evaluation	
	3.5	REGISTRATION PROCEDURES	
4.	TRE		10
	4.1	AZD2171-Prednisone Administration	10
	4.2	General Concomitant Medication and Supportive Care Guidelines1	01
	4.3	Duration of Therapy	
	4.4	Follow-up Criteria	12
	4.5	Off-Study Criteria	12
5.	DOS	SING DELAYS/DOSE MODIFICATIONS	
	5.1	Management of Hypertension	13
6.		/ERSE EVENTS: LIST AND REPORTING REQUIREMENTS	
		Comprehensive Adverse Events and Potential Risks List (CAEPR)	
		Expedited Adverse Event Reporting to Sponsor	
		NCI-IRB Expedited Adverse Event Reporting Requirements:	22
		NCI-IRB Requirements for PI Reporting of Expected and Unexpected Adverse Events	
		at Continuing Review	
		Routine Adverse Event Reporting	
	6.6	Secondary AML/MDS	22
-	БШ		00
7.	PHA		23
8.	001	RRELATIVE/SPECIAL STUDIES	0E
		Tissue Studies	
	8.1 8.2		-
	o.z 8.3	Imaging Studies	
	0.3	Assessment of the pharmacokinetic parameters of AZD2171	30
9.	сті		21
J .	310		JI
10	RA	EASUREMENT OF EFFECT	າວ
	. w 10.1	Definitions	-
	10.1	Guidelines for Evaluation of Measurable Disease	
	10.2	Response Criteria	
			50

## 1. OBJECTIVES

## 1.1. Primary

The primary objective of this study is to determine if AZD2171 is associated with a 30% 6 month probability of progression free survival in patients with metastatic AIPC as determined by clinical and radiographic criteria.

#### 1.2. Secondary

- 1.2.1 Measurement of overall response rate and overall survival. Response and progression will be evaluated in this study using the new international criteria proposed by the Response Evaluation Criteria in Solid Tumors (RECIST) Committee.
- 1.2.2 Document survival from the point of PSA progression in the absence of radiologic or clinical progression.
- 1.2.3 Demonstration of biologic effect by AZD2171 in the patient and on the tumor (when possible) via correlative studies will be conducted on serially obtained tissue biopsies, and dynamic contrast enhanced-magnetic resonance imaging (DCE-MRI). Laboratory correlates will include determining serum and tissue concentrations of Vascular Endothelial Growth Factor Receptor (VEGFR) as well as tissue microvessel density count.
- 1.2.4 Measurement of the pharmacokinetics of AZD2171 in human patients with prostate cancer.
- 1.2.5 Description of the prostate specific antigen (PSA) response rate to therapy with AZD2171

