## 4.3 Duration of Therapy

In the absence of treatment delays due to adverse event(s), treatment may continue until one of the following criteria applies:

- Radiographic disease progression,
- Intercurrent illness that prevents further administration of treatment,
- Unacceptable adverse event(s),
- Patient decides to withdraw from the study, or
- General or specific changes in the patient's condition render the patient unacceptable for further treatment in the judgment of the investigator.
- Patients who meet the criteria for PSA progression (See Section 10.5) may continue on study unless they meet the above criteria.

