# 9. STUDY CALENDAR

Baseline evaluations are to be conducted within 16 days prior to administration of protocol therapy. Scans and x-rays must be done 4 weeks prior to the start of therapy. In the event that the patient's condition is deteriorating, laboratory evaluations should be repeated within 48 hours prior to initiation of the next cycle of therapy. All patients will receive AZD2171 20 mg po daily and prednisone 10mg po daily. AZD-2171. AZD-2171 dose reductions will be made in 5 mg increments; the lowest dose level is dose level -2, or 10 mg. All baseline and follow up evaluations can be done on the last week of the prior cycle.

	Pre- Study	C1D1	C2D1	C3D1	C4D1	C5D1	Off Study
AZD2171 a		Х	Х	Х	Х	Х	
Prednisone a		Х	Х	Х	Х	Х	
Informed consent	Х						
Demographics	Х						
Medical history	Х						
Med List	Х	Х	Х	Х	Х	Х	Х
Physical exam	Х	Х	Х	Х	Х	Х	Х
Vital signs g	Х	Х	Х	Х	Х	Х	Х
Height	Х						
Weight	Х	Х	Х	Х	Х	Х	Х
Performance status	Х	Х	Х	Х	Х	Х	Х
CBC w/diff, plts, PSA	Х	Х	Х	Х	Х	Х	Х
Serum chemistry b	Х	Х	Х	Х	Х	Х	Х
Serum PAP	Х						
PKs h	Х	Х	Х	Х	Х	Х	
Serum Troponin T d	Х	Х	Х	Х	Х	Х	
TSH, free T4 e	Х	Х	Х				
EKG	Х	Х	Х	Х	Х	Х	
Urine dipstick for protein f	Х	Х	Х	Х	Х	Х	
Imaging studies c	Х		Х		Х		Х
Biomarkers	Х	Х	Х	Х	Х	Х	Х

a: AZD2171 and prednisone: Dose as assigned. Administered orally, daily at a fixed dose. Please keep a pill diary (Appendix B). Cycles = 28 days.

b: Albumin, alkaline phosphatase, total bilirubin, bicarbonate, BUN, calcium, chloride, creatinine, glucose, LDH, phosphorus, potassium, total protein, SGOT[AST], SGPT[ALT], sodium.

- c: CT, Bone scan, Echo, DCE-MRI and/or  FDG-PET. See Section 8.2.1.3 for the frequency of Imaging studies.
- d: Serum Troponin is to be obtained pre-study andonce a cycle thereafter.
- e: TSH and free T4 is to be obtained pre-study, once a cycle for the first two cycles, then only if clinically indicated.
- f: if patient has significant proteinuria, obtain a 24-hour urine for protein and creatinine clearance.

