## **10.5** Biochemical Response Criteria –PSA measurements (PSA Consensus Criteria) (Bubley et al. 1999)

- 10.5.1 PSA Decline of ≥50% A decline of PSA of at least 50% (confirmed by a second value at least 4 weeks after the first) with no other evidence of disease progression.
- 10.5.2. PSA Progression (all progression dates require to be confirmed by a second value after the first no sooner than 4 weeks after the initial measurement)

A 50% increase in PSA over nadir (confirmed by a second reading four weeks later) in patients whose PSA has fallen by at least 50%. PSA increase must be at least 5ng/ml.

- 10.5.2.1 A 25% increase in PSA over nadir (confirmed by a second reading) in patients whose PSA has not fallen by at least 50%. PSA increase must be at least 5ng/ml.
- 10.5.2.2 A 25% increase in PSA over baseline in patients whose PSA has not decreased. PSA increase must be at least 5ng/ml.
- 10.5.3 Time to PSA Progression

The time between the first day of treatment to the day of PSA progression as described in 9.5.2. the day of progression is defined as the first study day when the PSA level meets progression criteria (not the day of verification).

10.5.4 Patients will not be taken off trial for changes in PSA alone.

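### Survival after PSA progression (objective 1.2.2) is counted from the first PSA rise, but a man qualifies only after a confirming value at least 4 weeks later, so at least 28 days of survival are guaranteed

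*Protocol*

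**What the plan says.** Protocol 1.2.2 lists as a secondary objective: "Document survival from the point of PSA progression in the absence of radiologic or clinical progression". It does not define that point further.

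The dating comes from section 10.5. The heading line of 10.5.2 states the confirmation rule: "all progression dates require to be confirmed by a second value after the first no sooner than 4 weeks after the initial measurement". Section 10.5.3, under time to PSA progression, then fixes the date: "the day of progression is defined as the first study day when the PSA level meets progression criteria (not the day of verification".

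The individual criteria word confirmation unevenly. The last one, 10.5.2.2, reads "A 25% increase in PSA over baseline in patients whose PSA has not decreased" and does not mention a second value. The heading of 10.5.2 nevertheless covers every progression date.

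A PSA rise does not end treatment. Section 4.3 says: "Patients who meet the criteria for PSA progression (See Section 10.5) may continue on study unless they meet the above criteria". The study calendar (section 9) schedules PSA at the start of each cycle and at the off-study visit, with "Cycles = 28 days". Section 12.3 treats PSA endpoints as exploratory.

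**The concern.** Dating PSA progression to the first qualifying value suits time to PSA progression, where the progression is the event. In objective 1.2.2 the same date becomes time zero for survival. Whether a man belongs to the group is then settled by a measurement taken at least 4 weeks after his clock has started, so he must survive those weeks to be counted. This is immortal time. It comes with selection, because a man who dies before the second value is not classed as a progressor and his early death is not in the curve.

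The protocol keeps men on drug through PSA-only rises, and 1.2.2 is its planned description of how such men fare afterwards. The error runs in one direction: PSA-only progression looks more benign than it is.

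**Working it through.** **Inputs from the protocol**
- Time zero: first qualifying PSA (10.5.3, the only dating rule for PSA progression).
- Entry to the group: confirming PSA at least 4 weeks later (10.5.2).
- Routine PSA interval: one 28-day cycle (section 9).
- Survival after a PSA rise: not given. Medians M of 6, 9 and 12 months and two hazard shapes are assumed, only to show the range.

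**Guaranteed time**

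Confirmation date minus dated progression is at least 4 × 7 = 28 days. This is g = 28 / 30.4375 = 0.92 month and needs no assumption about survival. If the next routine value is missed and confirmation comes at 56 days, g = 1.84 months.

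**Effect on the median**

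The comparison is between the median from the first rise in all men with a rise (M) and the median from the first rise in those alive at g.

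*Constant hazard.* S(t) = exp(−ln 2 · t/M). Among men alive at g, the median solves t/M = 1 + g/M, so t = M + g.

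*Rising hazard (Weibull, shape 2).* S(t) = exp(−ln 2 · (t/M)²). Among men alive at g, the median solves (t/M)² = 1 + (g/M)², so t = √(M² + g²).

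| Assumed median M (months) | Constant hazard: M + g | Excess | Weibull shape 2: √(M² + g²) | Excess |
|---|---|---|---|---|
| 6 | 6.92 | +15.3% | √(36 + 0.846) = 6.07 | +1.2% |
| 9 | 9.92 | +10.2% | √(81 + 0.846) = 9.05 | +0.5% |
| 12 | 12.92 | +7.7% | √(144 + 0.846) = 12.04 | +0.3% |

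**Men who die before day 28 and are never classed as progressors**

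Under a constant hazard the share is 1 − exp(−ln 2 · g/M): 10.1%, 6.8% and 5.2% for M = 6, 9 and 12 months. Six-month survival would read 0.556 instead of 0.500, 0.676 instead of 0.630, and 0.746 instead of 0.707.

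The 28 guaranteed days are fixed by the definitions. How far they move the median depends on how many men die in those days, and the protocol gives no information on that.

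**The case against.** **The start date is inferred.** Section 1.2.2 does not say that its clock starts at the first value, and the wording that rules out the verification day sits under time to PSA progression. The time origin of a descriptive objective could be left to the SAP. This stands in part: the protocol never applies 10.5.3 to 1.2.2 in so many words. But 10.5.3 is the only rule there is, and it expressly rejects the confirmation date. An analyst who follows the protocol as written will inherit the bias, so this is a stated rule carried into the wrong use and not a missing detail.

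**The endpoint drives nothing.** It has no comparator, threshold or test, and no rule in section 12 uses it. This stands and sets the severity.

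**Stronger readings a reader might infer**
- *That the median is always overstated by at least 28 days.* This holds under a constant hazard but not under a rising one. Men free of clinical and radiologic progression, enrolled with a life expectancy above 3 months (3.1.5), may well have a low early hazard.
- *That the event-free survival in section 12.5 (57% at 3 months, 38% at 6 months) gives the share of men lost before confirmation.* Converted to 28 days it is 1 − 0.57^(0.92/3) = 15.8% or 1 − 0.38^(0.92/6) = 13.8%. Those figures describe the first 28 patients overall, not men followed from a PSA rise. The events are undefined there and may include PSA progression, which section 12 counts in one of its Kaplan-Meier analyses. Scans are at 0, 2 and 4 months and then every 3 months (8.2.1.3), so many 28-day spans contain none. The documents do not support this use.
- *That a man who progresses clinically or radiographically before confirmation can never be confirmed.* The calendar has an off-study PSA, which could confirm the rise if it falls at least 4 weeks after the first value. Leaving out men with such progression is also partly what 1.2.2 intends. What stays open is whether its absence is judged at the first or at the confirming value.

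**Conclusion.** The concern holds as a minor point. Read together, 10.5.2 and 10.5.3 give every man in the 1.2.2 analysis at least 28 days of guaranteed survival, and the resulting survival estimate is biased upward.

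The 28 days and the direction follow from the protocol alone. The effect on the median does not: it runs from about 1% or less (Weibull, shape 2) to 8–15% (constant hazard) over assumed medians of 6 to 12 months. No single figure within that range can be defended from the documents.

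The primary endpoint, the two-stage rule and the rules of the prednisone part are untouched.

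**What to change.** For objective 1.2.2 only:
- Start the survival clock on the date of the confirming PSA, in men alive and free of clinical and radiographic progression on that date. This also settles when the absence of progression is judged.
- Label the result survival after confirmed PSA-only progression.
- Report how many men had a first qualifying rise and then died, progressed or left before confirmation. The later start removes the guaranteed time but not this selection, so the count has to stand beside the curve.
- Keep the first-value date of 10.5.3 for time to PSA progression.

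The cost is a few sentences. The serial PSA values the plan already schedules supply both dates, and no visit, treatment or sample size changes. Each man's reported survival shortens by his own interval from first to confirming value, at least 28 days. The estimate then describes residual survival from confirmation, which is a different quantity from survival since the first rise.

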## 2. BACKGROUND

## 2.1 Androgen-independent Prostate Cancer

Prostate adenocarcinoma is the most common malignancy in American men and the second leading cause of cancer related deaths (Rini 2002; Jemal 2003). According to the SEER database, 42% of patients have either metastatic disease or will eventually progress following local therapy. Whereas androgen ablation therapy is an effective initial modality in patients with metastatic disease, androgen independence and progression of disease eventually occurs in all. (Goktas 1999; Klotz 2000). The utilization of second line hormonal agents is generally associated with low response rates, and has no documented survival benefit. Data from previous trials of NCI patients with similar eligibility requirements demonstrated a 2.1 month median progression free survival when using thalidomide (n=63) (Figg 2001). Median progression free survival on ketoconazole alone is expected to be 4 months based on previous trials (Oh 2002; Figg 2005).

Chemotherapies have been extensively evaluated in patients with metastatic androgen independent prostate cancer (AIPC) since the 1970s. The initial studies showed low response rates and high toxicities. Recently, however, with the development of new agents targeting prostate cancer both on the cellular and molecular level, promising results have been emerging. The agents, including docetaxel, mitoxantrone, estramustine, vinblastine and etoposide, either as a single agent or as a combination therapy, have produced significant PSA responses in 30-80% of patients with median progression free survival of 3-5 months (Beedassy 1999). Recently, two regimens containing docetaxel and either prednisone or estramustine have shown to have a significant increase in overall survival when compared to standard mitoxantrone/prednisone (Petrylak 2004; Tannock 2004). There is no standard therapy for patients who have progressed following docetaxel therapy. Plasma VEGF levels are significantly higher in patients with AIPC than in those with localized disease (Dugue 1999); in patients with AIPC, elevated pretreatment plasma VEGF inversely correlates with survival (George 2001). A recent study found an increasing plasma VEGF level gradient when healthy patients were compared to those with localized and metastatic disease (Shariat 2004). New therapeutic modalities are needed in patients with advanced AIPC. Siegal demonstrated that microvessel density was higher in prostate cancer tissue than the adjacent hypoplastic or benign tissue (Siegal 1995). Angiogenesis also has been shown to play an important role in prostate cancer progression (Sokoloff 1999, Choy 2001). Antiangiogenic therapy directed at the VEGF signaling axis may therefore be helpful in advanced AIPC.

## 2.2 AZD2171

AZD2171 (NSC 732208), an orally available small molecule, is a potent inhibitor of receptor tyrosine kinases (RTKs) which influence a key angiogenic factor, vascular endothelial growth factor-A (VEGF). VEGF is implicated in tumor blood vessel formation and in disease progression in a wide range of solid tumor malignancies. Expression of this factor is increased by diverse stimuli which include proto-oncogene activation and hypoxia, with the hypoxic state frequently occurring in solid tumors because of inadequate perfusion. In addition to its angiogenic role, VEGF also profoundly increases the permeability of the vasculature and thereby potentially contributes to tumor progression – a leaky tumor endothelium enhances nutrient and catabolite exchange and represents less of a barrier to tumor cell migration during metastasis. With the goal of suppressing neovascularization and thus inhibiting tumor growth and metastasis, numerous antiangiogenic agents have been developed. In contrast to many of these intravenously-administered antiangiogenic agents, a recently emerging class of novel orally-administered VEGF TK inhibitors including AZD2171 has been developed (Hennequin 1999; Wedge 2000, 2002).

Two high-affinity receptors for VEGF with associated TK activity have been identified on human vascular endothelium, KDR (kinase insert domain-containing receptor = VEGFR2) and Flt-1 (fms-like tyrosine kinase 1 = VEGFR1). Although the relative contributions of KDR and Flt-1 signaling in mediating tumor progression have not been elucidated, a number of studies suggest that KDR performs a predominant role. AZD2171 is a potent inhibitor of both KDR ( $IC_{50}$  < 0.002 microM) and Flt-1 ( $IC_{50}$  = 0.005 microM) and shows activity versus c-kit, platelet-derived growth factor receptor beta (PDGFR $\beta$ ), and Flt-4 at nanomolar concentrations, but is selective against other serine/threonine kinases studied. It has been shown that AZD2171 potently and selectively inhibits VEGF-stimulated human umbilical cord vascular endothelial cell (HUVEC) proliferation with an IC50 of 4 nM (Ogilvie 2004). These authors have also demonstrated the agent's profound inhibitory effect on vessel area, length, and branching at subnanomolar concentrations using a modified fibroblast/endothelial cell co-culture system. AZD2171's effects on hemodynamic parameters have been studied in an athymic rat xenograft model of human colorectal carcinoma (SW620) using perfusion-permeability dynamic contrast-enhanced magnetic resonance imaging (pp-DCE-MRI) (Bradley 2004). This method clearly demonstrated that in this model, AZD2171 significantly reduced vascular permeability by 80% (P<0.005) and vascular volume by 68% (P<0.05).

## Nonclinical Efficacy

The effect of AZD2171 was studied in athymic *nu/nu* mice bearing established subcutaneous human tumor xenografts of diverse histologies [SW620 (colon), PC-3 (prostate), Calu-6 (lung), SKOV-3 (ovarian), and MDA-MB-231 (breast)] (Wedge 2005). Animals were administered AZD2171 orally (PO) at doses from 0.75 to 6 mg/kg/day (2.25-18 mg/m^2/day) in a constant volume of 0.1 mL/10 g body weight for 24-28 days. AZD2171 produced a statistically significant inhibition of tumor growth in all human tumor types examined when dosed at 1.5 mg/kg/day (4.5 mg/m^2/day) or higher (Wedge 2005).

Angiogenesis and VEGF signaling play central roles in endochondral ossification. AZD2171 cased a dose-dependent increase in the hypertrophic chondrocyte zone of the epiphyseal growth plates in growing rats when dosed for 28 days. The effect was reversed upon withholding AZD2171. These results are consistent with the drug's ability to inhibit VEGF signaling and angiogenesis in this model (Wedge 2005).

The murine renal cell carcinoma (RENCA) model, which rapidly (generally within 10 days) metastasizes to the lung and abdominal lymph nodes, has also been used for AZD2171 efficacy studies (Drevs 2004). In experiments incorporating a vehicle control, AZD2171 (at a dose of 6.3 mg/kg/day PO) reduced primary tumor growth, metastasis, and microvessel density more potently than any other previously-studied VEGF RTK inhibitor reported in the literature.

Using a transgenic mouse model in which multiple mammary tumors spontaneously develop after two pregnancies, investigators studied the temporal effects of AZD2171 administration (Klinowska 2004). When dosed with AZD2171 (0.75 to 6 mg/kg/day PO) at the time early lesions start to develop, the number of tumor foci was not affected, but their growth was inhibited. When tumors were well established before AZD2171 was given (at doses of 3 and 6 mg/kg/day), dose-dependent growth inhibition occurred as well as tumor regression.

In another model, athymic *nu/nu* mice bearing human MCF-7 breast cancer xenografts were exposed to AZD2171. In this model, drug administration resulted in significant inhibition of tumor growth. This

inhibition was at least partially dependent on VEGF expression, as the drug effect was transient in tumors expressing VEGF (Miller 2006).

